1. INTRODUCTION

The purpose of this reporting and analysis plan (RAP) is to describe the analyses to be included in the Clinical Study Report for Protocol:

Protocol Revision Chronology:		
Original 2016N276451_00	28-Apr-2016	Original
Amendment Number 01 2016N276451_01	13-May-2016	
 ● Delete the contraceptive methods which can not be used in Japan.
Amendment Number 02 2016N276451_02	24-Jun-2016	
 ● Clarify the requirement for antibiotic administration which is needed before study treatment ● Change the criteria to perform the urine culture/sensitivity test ● Change the definition of urinary tract infection partially in this study ● Change the adverse event term at increased residual urine volume
Amendment Number 03 2016N276451_03	07-Sep-2016	
 ● Change the part of exclusion criteria for the use of intravesical pharmacological agent ● Clarify the day of re-treatment criteria regarding the duration of antibiotic administration ● Clarify the intravesical pharmacological agent as a prohibited medication ● Clarify the initiation of clean intermittent catheterization and definition of urinary retention as an adverse event
Amendment Number 04 2016N276451_04	14-Apr-2017	
 ● Change the inclusion criteria, and add the exclusion criteria and the stratification factor since spinal cord injury patient with neurological injury level C5 to C8 is added as the new candidate for this study. ● Change the use of general anesthesia partially since spinal cord injury patient with neurological injury level C5 to C8 is added as the new candidate for this study. ● Change the inclusion criteria since patient currently uses temporary indwelling balloon catheter is to be

		
included in this study.
 
 ● Add the cholinesterase inhibitor for the treatment of urinary disturbance as the prohibited medication ● Change the schedule of sample collection for neutralizing antibody partially
Amendment Number 05 2016N276451_05	20-Jul-2017	
 ● Extend the study period
Amendment Number 06 2016N276451_06	16-Nov-2017	
 ● Change the medical monitor/sponsor information page ● Extend the study period

2. SUMMARY OF KEY PROTOCOL INFORMATION

2.1. Changes to the Protocol Defined Statistical Analysis Plan

Changes from the originally planned statistical analysis specified in the protocol are outlined in [Table 1](#).

Table 1 Changes to Protocol Defined Analysis Plan

Protocol	Reporting & Analysis Plan	
Statistical Analysis Plan	Statistical Analysis Plan	Rationale for Changes

To use MMRM and ANCOVA for percent change from baseline in
 
 • Daily average number of urinary incontinence • Average volume voided per void • Daily average number of voids 	
To provide only summary statistics, not statistical analyses.
	
Upon blind review for endpoints of percent change from baseline, it was considered that normality assumptions are violated for percent change from baseline in "Daily average number of urinary incontinence". Therefore, it is not appropriate to apply MMRM/ANCOVA for these endpoints and only summary statistics will be provided. To be consist with this change, only summary statistics of percent change from baseline in "Average volume voided per void" and "Daily average number of voids" will be provided without any statistical analyses.

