### 9.4.2. Secondary Analyses

#### Efficacy

The following endpoints until week 12 after the first treatment will be analyzed using MMRM. This model will include the treatment group, visit, patient etiology and treatment-by-visit interaction as fixed factors and baseline values and baseline-by-visit interaction as a covariate. The treatment differences after week 12 after the first treatment will be analyzed using analysis of covariance (ANCOVA) model at each visit. This model will include the treatment group, patient etiology as fixed factors, and baseline values as a covariate. Least-squares mean and its two-sided 95% confidence intervals will be estimated.

- Change from baseline and percent change from baseline:
  - Daily average number of urinary incontinence episodes (except for change from baseline at week 6 after the first treatment)
  - Average volume voided per void
  - Daily average number of voids

The following endpoints will be analyzed using ANCOVA model at each visit. This model will include the treatment group, patient etiology as fixed factors, and baseline values as a covariate. Least-squares mean and its two-sided 95% confidence intervals will be estimated.

- Change from baseline
  - Urodynamic assessment
    - Maximum cystometric capacity (MCC)

- Maximum detrusor pressure during the first involuntary detrusor contraction (IDC) ( $P_{\max\text{IDC}}$ )
- Volume at first IDC ( $V_{P_{\max\text{IDC}}}$ )
- Maximum detrusor pressure during the storage phase ( $P_{\text{detMax}}$ )
- King's Health Questionnaire (KHQ) domain score

The following endpoints will be summarized by visit. Odds ratio and its two-sided 95% confidence intervals will be estimated.

- Proportion of subjects attaining 100%,  $\geq 75\%$  and  $\geq 50\%$  reduction from baseline in the daily average of urinary incontinence episodes
- Proportion of patients with positive response on the TBS

Duration of treatment effect will be evaluated for each treatment group in 2 different ways.

- Time to the subject's first qualification for 2nd treatment from the day of 1st treatment
- Time to the subject's first request for 2nd treatment from the day of 1st treatment (regardless of fulfilment of the re-treatment criteria)

The time to event will be graphically displayed as Kaplan-Meier curves. Time to request/qualification for 2nd and 3rd treatment will not be analyzed.

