7.2.2. Summary Measure

Mean treatment difference or odds ratio by visit, or hazard ratio for double blind period.

No treatment comparison for open label period.

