
 The endpoints will be analyzed using an analysis of covariance (ANCOVA) model. Terms fitted in the ANCOVA model will include: 
 Fixed, categorical effects: treatment Fixed, continuous effects: baseline value Since the numbers of subjects of both SCI with neurological injury level C5 to C8 and MS are small, NDO etiology will not be included in MMRM, as described in study protocol. The Kenward-Roger option in SAS PROC MIXED will be used to estimate denominator degrees of freedom and standard errors.
Model Results Presentation

 Adjusted means (LS means) and corresponding SEs of means will be presented for each treatment by visit, together with estimated treatment differences (GSK1358820 – Placebo), the corresponding 95% confidence intervals.

Secondary Statistical Analyses for change from baseline after first treatment
Endpoint(s)

 Change from baseline at week 6 after the first treatment 
 Maximum cystometric capacity (MCC) Maximum detrusor pressure during the first involuntary detrusor contraction (IDC) ($P_{\max IDC}$) Volume at the first involuntary detrusor contraction ($V_{P_{\max IDC}}$) Maximum detrusor pressure during the storage phase ($P_{\det Max}$) KHQ domain score (role limitations, social limitations)
Model Specification

 Same as “Secondary Statistical Analyses for change from baseline after week12 after first treatment”.
Model Results Presentation

 Same as “Secondary Statistical Analyses for change from baseline after week12 after first treatment”.

Secondary Statistical Analyses for Binary data
Endpoint(s)

 Proportion of subjects attaining 100%, $\geq 75\%$ and $\geq 50\%$ reduction from baseline in the daily average of urinary incontinence episodes Proportion of subjects with positive response on the TBS
Results Presentation

 The number and percent of subjects who met each endpoint will be summarized by treatment and visit. The odds ratio and its 95% confidence interval will also be presented.
Missing Data

 Missing data until week 12 after first treatment will be treated as non-responder or no positive response. Missing data after week 12 after first treatment will be treated as missing.

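### SAP 2.1 replaces the planned between-arm estimate of percent change with per-arm summaries for three secondary endpoints, and non-normality in one of them does not justify giving none

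*SAP*

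**What the plan says.** Protocol 9.4.2 sets out the model for the diary endpoints: "The following endpoints until week 12 after the first treatment will be analyzed using MMRM", followed by ANCOVA at each later visit, with least-squares means and 95% CIs. The quantities to be modelled are given as "Change from baseline and percent change from baseline" for incontinence episodes, volume per void and number of voids.

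SAP 2.1, Table 1 changes this for percent change: "To provide only summary statistics, not statistical analyses". The reason is that, on blinded review, "it was considered that normality assumptions are violated for percent change from baseline in" the incontinence measure, from which the SAP concludes: "Therefore, it is not appropriate to apply MMRM/ANCOVA for these endpoints and only summary statistics will be provided". For volume per void and number of voids, summary statistics "will be provided without any statistical analyses", so as to match. No distributional finding is reported for those two.

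Percent change stays in the endpoint lists of SAP 2.2 and 7.2.1. In SAP 7.2.5.1 the MMRM and ANCOVA blocks list absolute change only. Tables 2.3, 2.14 and 2.25 are descriptive displays, and SAP 11.5.2 defines a continuous summary by per-arm quantities (N, mean, SD or SE, median, range). No transformation, rank method or median difference appears anywhere. The only between-arm estimates left on the relative scale are the odds ratios for 100%, at least 75% and at least 50% reduction in incontinence.

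**The concern.** Non-normality is a reason not to fit a normal-theory model to a skewed or bounded outcome. It is not a reason to give no treatment difference, because distribution-free estimates with intervals are available. The SAP moves from the first statement to the second without considering an alternative.

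The double-blind cycle is the only placebo-controlled part of the trial. SAP 7.2 limits the open-label phase to summaries because no comparison is wanted there; percent change in the double-blind cycle now gets the same treatment. The trial tests no hypotheses, so estimates and intervals are what it delivers. Three endpoints that the plan still names would be reported without either. For two of them the only reason given is consistency with the third.

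**Working it through.** **1. What remains, by measure (TC1, between-arm)**

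| Measure | Absolute change | Percent change: planned | Percent change: SAP | Responder odds ratio |
|---|---|---|---|---|
| Incontinence | MMRM/ANCOVA | MMRM/ANCOVA | none | 50%, 75%, 100% |
| Volume per void | MMRM/ANCOVA | MMRM/ANCOVA | none | none |
| Number of voids | MMRM/ANCOVA | MMRM/ANCOVA | none | none |

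**2. The plan's own figure.** Protocol 9.2.1 uses 15 per arm, a difference of -1.5, SD 3.0 and two-sided 5%. SE = 3.0 × √(2/15) = 1.095; noncentrality = 1.5/1.095 = 1.369; the noncentral t with 28 df gives 26.2%, matching the stated 26%. The directional probability is Φ(1.369) = 91.5%, or 92.6% with the separate SDs of 3.10 and 2.56; the protocol says about 92%. Both figures concern absolute change. The documents give no SD or responder rate for percent change, so steps 3 and 4 are illustrations.

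**3. No baseline assumed.** Latent normal outcome, effect 1.5/3.0 = 0.5 SD, 15 per arm, 20,000 simulated trials. Chance that the test or 95% CI excludes no effect:
- t-test: about 26%
- Wilcoxon: about 24%
- Wald odds ratio, cut at or 0.5 SD below the placebo mean: 15-16%
- Wald odds ratio, cut 1.0 SD below: 5%; 1.5 SD below: 0.2%

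**4. On the percent scale.** Change is Normal with SD 3.0 and a between-arm difference of 1.5. Post-treatment values are floored at 0 and rounded to thirds for the 3-day diary. Assumed: median baseline 3, 4.5 or 6 episodes/day, and placebo mean change -0.5, -1.0 or -1.5. The minimum baseline of 2 follows from inclusion criterion 5 (6 episodes over 3 days, 6/3 = 2). Ranges span the nine scenarios and repeated runs of at least 4,000 trials each:

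| Comparison | Chance of excluding no effect |
|---|---|
| Wilcoxon on percent change | about 20-23% |
| Odds-ratio 95% CI, 50% cut | about 7-16% |
| Odds-ratio 95% CI, 75% cut | about 1-16% |
| Odds-ratio 95% CI, 100% cut | about 0-13% |
| ANCOVA on absolute change (retained) | about 20-25% |

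The SAP does not state how the odds-ratio interval is computed. Wald intervals were used, and tables with a zero cell were counted as not excluding 1. With a Pearson chi-square at the 50% cut instead (15-17%), the advantage of ranks is about 4-7 points.

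**5. Sparse cells at the 100% cut.** With 15 per arm, placebo rate p and active rate q, P(at least one zero cell) = 1 - (1 - (1-p)^15 - p^15)(1 - (1-q)^15 - q^15). For assumed q of 20-50% this is 46-48% at p = 5%, 21-23% at p = 10% and 4-7% at p = 20%.

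**6. Limit of a shift estimate.** Incontinence percent change cannot fall below -100%. In the step 4 set-up, 14-47% of active and 7-30% of placebo subjects sit exactly at that bound.

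**The case against.** The strongest reply is that percent change rescales measures that are already compared with placebo on the full scale, with baseline adjustment, and that the retained analysis is at least as sensitive. That stands. A reader might infer from Table 1 that the placebo comparison is lost for volume per void and number of voids; SAP 7.2.5.1 shows that it is not.

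Three other stronger readings also fail:
- That the SAP dichotomised because of non-normality. The responder proportions were a separate secondary endpoint in the protocol, with odds ratios already planned.
- That SAP 7.2.2 promises a between-arm measure for every secondary endpoint. Its wording, "Mean treatment difference or odds ratio by visit, or hazard ratio for double blind period", is a generic list. It names a hazard ratio although 7.2.5.1 applies no model to the time-to-event data.
- That the MMRM could simply be kept for the two endpoints with no reported violation. The SAP publishes no diagnostics for them, so silence is not evidence of normality.

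It is also fair that the change was made on blinded data, is disclosed with a rationale, and leaves per-arm medians visible. A Hodges-Lehmann estimate is not baseline-adjusted, and ties at -100% weaken its reading as a pure shift. These points limit the stakes. They do not supply a reason for giving no interval.

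**Conclusion.** The point holds, at modest size. The protocol planned a between-arm estimate with 95% CI for three named endpoints. The SAP removes all three on a finding reported for one, and offers no distribution-free substitute. What is lost is estimation on the percent scale only.

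The primary endpoint, absolute change and the responder analyses are unaffected, and the trial makes no formal test. A rank comparison is more sensitive than the 50% odds ratio (about 20-23% against 7-16%), but not more than the retained absolute-change analysis (20-25%), so it would be wrong to present the change as a power gain. The simulated figures rest on assumed baselines, assumed placebo response and Wald intervals; the textual finding rests on none of these. It is a cheap improvement rather than a defect in the main result.

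**What to change.** In SAP 2.1 Table 1, SAP 7.2.5.1 and Tables 2.3, 2.14 and 2.25, add for TC1 at Weeks 2, 6 and 12 the Hodges-Lehmann between-arm difference (GSK1358820 minus placebo) with its rank-based 95% CI, for all three percent-change endpoints, using observed data without imputation. Label it descriptive. Add a footnote that incontinence percent change is bounded at -100%, so ties there limit a location-shift reading. Leave the responder odds ratios as planned, with their own missing-data rule.

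The addition stops at Week 12, so the protocol's later ANCOVA of percent change stays dropped. After Week 12, re-treated subjects leave TC1, so the arms are no longer complete.

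Cost: SAP wording and one block in three existing tables, with no new data. The downside is a few more unadjusted descriptive intervals (3 endpoints × 3 visits = 9) in a plan that already makes no multiplicity adjustment.

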2.2. Study Objective(s) and Endpoint(s)

Objectives	Endpoints
Primary Objective	Primary Endpoint

 To evaluate the efficacy of a single dose treatment of GSK1358820 200 U 	
 Change from baseline in the daily average number of urinary incontinence episodes at week 6 after the first treatment.
Secondary Objectives	Secondary Endpoint

 To evaluate the efficacy of a single dose treatment of GSK1358820 200 U compared with placebo To evaluate the efficacy of repeated dose treatment of GSK1358820 200 U 	
 Changes from baseline at week 6 after the first treatment in the following endpoints by urodynamic assessment 
 Maximum cystometric capacity (MCC) Maximum detrusor pressure during the first involuntary detrusor contraction (IDC) ($P_{\max\text{IDC}}$) Volume at first IDC ($V_{P_{\max\text{IDC}}}$) Maximum detrusor pressure during the storage phase (P_{detMax}) Changes from baseline and percentage change from baseline in the following endpoints 
 Daily average number of urinary incontinence episodes Daily average number of voids Average volume voided per void Proportion of patients attaining 100%, $\geq 75\%$ and $\geq 50\%$ reduction from baseline in the daily average of urinary incontinence episodes Duration of treatment effect after 1st treatment 
 Time to qualification for retreatment Time to request for retreatment Health outcome 
 Changes from baseline in King's Health Questionnaire (KHQ) domain score Proportion of patients with positive response on the Treatment Benefit Scale (TBS)

 To evaluate the safety of a single dose treatment of GSK1358820 200 U compared with placebo To evaluate the safety of a repeated dose treatment of GSK1358820 200 U 	
 Adverse events Safety parameter 
 Vital signs and physical examination Clinical laboratory (hematology, blood chemistry and urinalysis) Urine culture and sensitivity Post void residual (PVR) urine volume Use of clean intermittent catheterization

Objectives	Endpoints
	(CIC) for urinary retention / elevated PVR [Only patients who are able to spontaneously void (excluding mixed catheterization) at baseline] 
 • Kidney and bladder ultrasound • Pregnancy test • Twelve-lead electrocardiogram (ECG)
Other Objectives	Other Endpoints

 • To evaluate the existence of toxin-neutralizing antibody after the treatment of GSK1358820 200U 	
 • Neutralizing antibody measurement

Note: “Daily average” means “Daily frequency calculated by 3-day dairy”. More detail for calculation methods will be in section [11.6.3](#).

2.3. Study Design

Overview of Study Design and Key Features	

Screening Within 4wk 0 2 6 12 42 48(wk)
 
1st treatment period (DB) 2nd treatment period (OL)
 
GSK1358820 200U or Placebo GSK1358820 200U
 
injection : ↑ ← Reinjection period →
 
Retreatment: Max 2 times at least 12 wks interval (if retreatment criteria fulfill) Study visit: Subject visits at week 2, 6 and 12 after the first treatment and then are conducted alternately visit or verification by tel every 6 weeks until week 48 (exit) If subject is retreated, subject visits at week 2, 6 and 12 after each retreatment and then are conducted alternately visit or verification by tel every 6 weeks until exit at week 48 after the initial treatment
	
Design Features	
This study includes a Screening phase, a Treatment phase 1(double-blind treatment phase), and a Treatment phase 2 (open-label treatment phase). The study design of each treatment phase is shown below.
 
 • Treatment phase 1: Multicenter, randomized, double-blind, placebo-controlled, parallel-group comparison design • Treatment phase 2: Multicenter, open-label design
Dosing	
 • Subjects meeting the eligibility criteria will be randomly assigned by the registration center to one of the 2 treatment arms (either 200 U GSK1358820 or placebo) in a ratio of 1:1. Subsequently, in Treatment phase 1, subjects will receive single treatment with the allocated study drug (30 injections each of 1.0 mL) which will be injected into the detrusor muscle of bladder. • Subjects who meet the criteria for re-treatment between 12 to 36 weeks after 1st treatment will enter to Treatment phase 2 to receive re-treatment. Subjects are permitted to receive re-treatment until up to 36 weeks after 1st treatment and at most 2 times
Treatment Assignment	
 • Number of subjects (randomized subjects): 30 (15 per group) • GSK RandAll NG will be used to generate the randomization schedule. • The randomization will be stratified by NDO etiology (SCI with neurological injury level C5 to C8, SCI with neurological injury level T1 or below, or MS).
Interim Analysis	
 • Interim analysis is planned in this study as described in 3.1.

2.4. Statistical Hypotheses / Statistical Analyses

This study is not designed to evaluate formal statistical hypotheses.

3. PLANNED ANALYSES

3.1. Interim Analyses

The interim planned primary analyses will be performed after the completion of the following sequential steps:

1. All subjects have completed treatment phase 1 (or week 24 of treatment phase 1, except for the premature withdraw) as defined in the protocol.
2. If the subject completes treatment phase 1 and receives 2nd treatment, this subject should have completed the visit corresponding to 24 weeks after 1st treatment.
 - The subject who completed Week 12 visit and was re-treated at a visit before Week 18 in treatment phase 1 should complete the Week 12 visit in treatment phase 2.
 - The subject who completed Week 18 visit and was re-treated at a visit before Week 24 in treatment phase 1 should complete the Week 6 visit in treatment phase 2.
3. All required database cleaning activities have been completed and interim database release (DBR) and database freeze (DBF) has been declared by Data Management.
4. All criteria for unblinding the randomization codes have been met.
5. Randomization codes have been distributed according to RandAll NG procedures.

The interim analyses will be performed for regulatory submission. However subject level data will not be disclosed to people who work at the sites including investigators.

In interim analyses, the following analyses will be done with datasets which will include data until 24 weeks after 1st treatment.

- Study population
- Efficacy and safety analyses for treatment cycle (TC) 1 (except for time to event analyses)
- Safety analyses for Overall period (i.e., the analyses for population “SP1”, which include subjects who had at least one GSK1358820 treatment)

3.2. Final Analyses

The final planned primary analyses will be performed after the completion of the following sequential steps:

1. All subjects have completed the study as defined in the protocol.
2. All required database cleaning activities have been completed and final DBR and DBF has been declared by Data Management.

4. ANALYSIS POPULATIONS

Population	Definition / Criteria	Analyses Evaluated
Screened	
 Comprise all screened subjects 	
 Study Population
Enrolled	
 All participants who passed screening and entered the study. Included are: only Randomized Participants Note screening failures (who never passed screening even if rescreened) are excluded from the Enrolled population as they did not enter the study. 	
 Study Population
Full Analysis Set 1 (FAS1)	
 Comprise all randomized subjects who have at least 1 post-baseline efficacy assessment. This population will be based on the treatment to which the subject was randomized (this will be applied to FAS2 and FAS3). Any subject who receives a treatment randomization number will be considered to have been randomized. 	
 Study Population Efficacy for the TC 1 (double blind phase)
Full Analysis Set 2 (FAS2)	
 Comprise all randomized subjects who have at least 1 post-2nd treatment efficacy assessment after 2nd treatment. 	
 Efficacy for the TC 2
Full Analysis Set 3 (FAS3)	
 Comprise all randomized subjects who have at least 1 post-3rd treatment efficacy assessment after 3rd treatment. 	
 Efficacy for the TC 3
Safety for double blind phase (SPDB)	
 Comprise all subjects who receive at least one dose of study treatment. This population will be based on the treatment the subject actually received (this will be applied to all safety population). 	
 Safety for the TC 1 (double blind phase)
Safety 1 (SP1)	
 Comprise all subjects who receive at least one dose of GSK1358820 	
 Safety for at least one dose of GSK1358820 treatment
Safety 2 (SP2)	
 Comprise all subjects who receive at least two doses of GSK1358820 	
 Safety for two doses of GSK1358820 treatment
Safety 3 (SP3)	
 Comprise all subjects who receive three doses of GSK1358820. 	
 Safety for three doses of GSK1358820

Population	Definition / Criteria	Analyses Evaluated
		treatment

NOTES :

- Please refer to [Appendix 10: List of Data Displays](#): List of Data Displays which details the population to be used for each display being generated.

